4.2 SCIENTIFIC RATIONALE FOR STUDY DESIGN

Randomized control trials are known to be the least biased form of evidence. The factorial design of this trial is efficient, allowing us to perform two randomized trials simultaneously. It is very unlikely that there will be an interaction between surgery and ripasudil. All patients will receive standard of care treatment.

DETECT

Version 5.0
21 March 2023

4.3 JUSTIFICATION FOR DOSE

Route of administration and dosage of topical ripasudil 0.4% are consistent with previous studies of the drug. Topical placebo will be administered in the same way as topical ripasudil to mask the patient, physician, and study staff. The topical placebo solution will have the same clear appearance as ripasudil to maintain masking.

4.4 END OF STUDY DEFINITION

A participant is considered to have completed the study if he or she has completed all phases of the study including the final 24-month visit, as shown in the Schedule of Activities (SoA), **Section 1.3**.

5 STUDY POPULATION

5.1 INCLUSION CRITERIA

In order to be eligible to participate, an individual must meet all of the following criteria:

DETECT I

- Dysfunctional endothelium from Fuchs Endothelial Corneal Dystrophy (FECD) with guttata extending beyond 4.5 mm of the central cornea or severe edema without visualization of guttata
- Dysfunctional endothelium from Pseudophakic Corneal Edema (PCE) or Iridocorneal Endothelial Syndrome (ICE) or other primary endothelial dysfunction such as Posterior Polymorphous Corneal Dystrophy (PPMD)
- Dysfunctional endothelium from prior graft failure after PKP or EK
- Controlled uveitis (defined as quiet for > 3 months off topical steroids with or without systemic immunosuppression) or no uveitis
- Controlled glaucoma with topical medications and/or prior trabeculectomy or tube shunt without ongoing hypotony (IOP < 5 mmHg) or no glaucoma
- Good candidate for corneal transplantation for either DMEK or UT-DSAEK
- Willingness and ability to undergo corneal transplantation
- Willingness to consistently use study medications (i.e. ROCK-inhibitors)
- Willingness to participate in follow-up visits
- Age greater than 18 years

DETECT II

- Dysfunctional endothelium from FECD with few guttata extending beyond 4.5 mm
- Peripheral endothelial cell count >1500 cells/mm²
- Good surgical candidate for either procedure as determined by the surgeon
- Willingness and ability to undergo corneal transplantation
- Willingness to consistently use study medications (i.e. ROCK-inhibitors)
- Willingness to participate in follow-up visits
- Age greater than 18 years

5.2 EXCLUSION CRITERIA

An individual who meets any of the following criteria will be excluded from participation in this study:

DETECT I

- Aphakia, or anterior chamber IOL or scleral fixated IOL in study eye prior to or anticipated during EK
- Pre-operative central sub-epithelial or stromal scarring that the investigator believes is visually significant and could impact post-operative stromal clarity assessment

DETECT

Version 5.0
21 March 2023

- Peripheral anterior synechiae (iris to angle) in the angle greater than a total of three clock hours
- Visually significant optic nerve (ok to have small visual field defects) or macular severe pathology
- Inability to comply with post-operative instructions (i.e. unable to position)
- Pregnancy
- Cataract surgery within the last 3 months
- Fellow eye visual acuity <20/200

DETECT II

- Other primary endothelial dysfunction such as PPMD
- Any prior intraocular surgery other than cataract surgery
- Cataract surgery within the last 3 months
- >3 clock hours of ANY anterior or posterior synechiae
- >1 quadrant of stromal corneal vascularization
- Visually significant optic nerve or macular pathology
- Fellow eye visual acuity <20/200
- Pregnancy
- Inability to comply with post-operative instructions (i.e. unable to position)
- Hypotony (Intraocular pressure <10mmHg)
- Peripheral anterior synechiae (iris to angle) in the angle greater than a total of three clock hours
- Aphakia, or anterior chamber IOL or scleral fixated IOL in study eye prior to or anticipated during EK
- Pre-operative central sub-epithelial or stromal scarring that the investigator believes is visually significant and could impact post-operative stromal clarity assessment

5.2.1 PREGNANCY EXCLUSION:

Women of childbearing age will have to take a urine test prior to enrolling in the study. Women of childbearing age will need to use birth control while taking Ripasudil. Women will check with their doctor about what kind of birth control methods to use and how long to use them. For this study women of childbearing age would only need to use birth control for the three months of taking Ripasudil.

Pregnancy is a contraindication to Ripasudil. If participant gets pregnant during treatment with ripasudil they will need to stop taking it. Participant will continue in study but will not be on ripasudil. We will follow the patient until the end of the study.

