5.4 SCREEN FAILURES

Screen failures are defined as participants who consent to participate in the clinical trial but are not subsequently randomly assigned to the study intervention or entered in the study. A minimal set of screen failure information is required to ensure transparent reporting of screen failure participants, to meet the Consolidated Standards of Reporting Trials (CONSORT) publishing requirements and to respond to queries from regulatory authorities. Minimal information includes demography, screen failure details, eligibility criteria, and any serious adverse event (SAE).

In this study, all patients who are randomized will be included in the primary analysis, regardless of whether or not they actually receive the assigned intervention. Randomization will occur just days before the participant's surgery to ensure that all randomized patients receive their assigned surgical intervention. Due to the nature of the intervention, patients may have weeks to months between enrollment in the study and randomization/surgery, leaving time for patients to drop out of the study before randomization. All required information will be collected from screen failures.

DETECT

Version 5.0
21 March 2023

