6 STUDY INTERVENTION

6.1 STUDY INTERVENTION(S) ADMINISTRATION

6.1.1 STUDY INTERVENTION DESCRIPTION

Ultrathin Descemet stripping automated endothelial keratoplasty (UT-DSAEK)

Tissue grafts will be cut to the right thickness using a microkeratome prepared at the eye bank per standard eye bank protocol (about 60-90 microns). The grafts will be punched in the operating room to 7.0- 7.5 mm. A 4 mm corneal incision will be used, with Endoserter as the means of inserting the graft, an FDA approved device for this purpose. Donor tissue or media will be sent for fungal culture by the enrollment site.

Descemet membrane endothelial keratoplasty (DMEK)

Endothelial grafts will be pre-peeled at the eye bank, pre-punched to 7.0 - 7.5 mm and pre-loaded at the eye bank. The endothelium will be stained with trypan blue. The recipient descemets membrane will be stripped to 7.0 - 7.5 mm. A 2.4 mm corneal incision will be used and the graft will be inserted with a modified Jones tube injector, micro Jones tube injector, LEITR glass cannula, micro Stephens glass cannula, or Geuder cannula. The tap technique will be used to position the graft. Donor tissue or media will be sent for fungal culture by the enrollment site.

Descemet Stripping Only (DSO)

The pupil center will be marked in mesopic conditions to guide centration. A 4mm diameter imprint centered on the central mark will be used to guide the descemetorhexis. A reverse sinskey hook will be used to gently initiate a tear in Descemet's membrane and Gorovoy DSO forceps (or similar instrument) will be used to complete the descemetorrhexis

DETECT

Version 5.0
21 March 2023

without disturbing the underlying stroma. The central endothelium will then be gently peeled and removed with forceps.

Ripasudil 0.4%

Ripasudil 0.4% is a selective rho-kinase (ROCK) inhibitor that has been shown to promote endothelial cell proliferation. Patients randomized to receive topical ripasudil will begin medication on post-op day 1. They will take this medication 4 times per day for 3 months.

Placebo

For participants randomized to placebo, they will receive topical placebo in place of topical ripasudil. The placebo will be sodium chloride 0.9%. Those randomized to placebo will receive the topical placebo on the same medication schedule described above for ripasudil.

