8.3.9 REPORTING OF PREGNANCY

Women of childbearing age (ie women who have been told by their doctors that they need to take birth control to avoid pregnancy) will be required to take a urine test prior to enrolling in the study. Women of childbearing age will need to use birth control while taking Ripasudil. Women will check with their doctor about what kind of birth control methods to use and how long to use them. For this study women of childbearing age would only need to use birth control for the three months of taking Ripasudil.

There is no available data on the risk of taking Ripasudil during pregnancy; however, the systemic absorption from a topical eye drop is low. If a participant gets pregnant while taking the study drug, they will stop taking the study drug. Participants will continue in study and we will follow the patient until the end of the study- regardless of their ability to continue the study drug.

DETECT

Version 5.0
21 March 2023

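### The pregnancy test and contraception rules leave the wait between enrolment and the first dose of ripasudil uncovered; a small safety gap that is cheap to close

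*Protocol*

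**What the plan says.** Pregnancy is an exclusion criterion in both DETECT I and DETECT II. Section 5.2.1 states that "Pregnancy is a contraindication to Ripasudil", and section 8.3.9 adds that no data exist on the risk of using it in pregnancy.

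The safeguards written into the protocol are these:

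- **Test.** Section 5.2.1: "Women of childbearing age will have to take a urine test prior to enrolling in the study". Section 8.3.9 repeats the same time point. The Schedule of Activities (section 1.3) has no pregnancy-test row at any visit.
- **Contraception.** Section 8.3.9 says that women of childbearing age "would only need to use birth control for the three months of taking Ripasudil"; section 5.2.1 says the same.
- **Stop rule.** Section 5.2.1: "If participant gets pregnant during treatment with ripasudil they will need to stop taking it".

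On timing, section 5.4 says that "patients may have weeks to months between enrollment in the study and randomization/surgery". Section 6.1.1 says: "Patients randomized to receive topical ripasudil will begin medication on post-op day 1".

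**The concern.** The rules cover two points in time: entry to the study and the three months of treatment. They do not cover what lies between. A woman who tests negative at enrolment and conceives while waiting for surgery is already pregnant when the drops begin. The entry test came too early to find her, no study contraception was required of her at that time, and the stop rule is worded for a pregnancy that begins during treatment.

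At stake is exposure of an unrecognised early pregnancy to a drug for which the protocol reports no pregnancy data. This is a participant-safety and eligibility matter. It does not bear on the estimand, the sample size or the error rates.

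The contraception rule is also hard to apply as worded. It is tied to taking ripasudil, but participants and physicians are masked to the study medication, so a woman cannot know whether the rule applies to her.

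**Working it through.** The plan gives no figure to reproduce. The check consists of placing the timing rules side by side, followed by a rough sizing.

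**1. Length of the uncovered interval**

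- Schedule of Activities: enrolment and baseline are on Day 0, and surgery is on Day 5 with a window of 14 days either way. Latest surgery: 5 + 14 = Day 19. First dose on the first post-operative day: 19 + 1 = Day 20.
- Section 5.4: weeks to months from enrolment to randomisation and surgery.

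The two sources differ on how long the wait can be, but both leave an interval before the first dose with neither a required test nor required contraception.

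**2. Whether anything else in the protocol closes it**

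- Section 5.2.1 tells women to ask their doctor how long to use contraception. The next sentence limits the study requirement to the three months on ripasudil.
- Section 6.2.5 has the drops shipped several days before surgery, after which the site confirms receipt and reviews instructions. No negative test is a condition of shipping or starting them.
- Section 7.1 leaves the response to a clinically significant finding after enrolment to the investigator. That helps once a pregnancy is known; it does not detect one.

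**3. Rough size**

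The protocol does not say how many women of childbearing age it expects, and gives no conception rate. As assumptions, take a wait of 20 days (the schedule's upper limit) to 90 days (one reading of section 5.4) and 5% to 15% conceptions per woman-year. The chance per woman = (days / 365) × annual rate:

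- Low: 20/365 × 0.05 = 0.003
- High: 90/365 × 0.15 = 0.037

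Even at the high end, one expected conception before dosing would need 1/0.037, or about 27, such women on ripasudil. Half of 160 plus half of 60 gives 80 + 30 = 110 participants on ripasudil, so 27 would be about 25% of them (27/110 = 0.245). The expected age distribution (section 1.1: median 67, interquartile range 64 to 71) puts only about a quarter of participants of either sex below 64. The expected number is therefore well below one.

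**4. How near the first dose a repeat test would fall**

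Section 5.5 puts randomisation one week before surgery, and section 6.3 puts it 1 to 3 weeks before. A test done just before randomisation is then 7 + 1 = 8 days to 21 + 1 = 22 days before the first dose. A repeat test alone still leaves some days open, which is why the contraception period also has to start earlier.

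**The case against.** The strongest case against the point is that it hardly matters. The expected population is elderly. Section 8.3.9 narrows the group to "women who have been told by their doctors that they need to take birth control to avoid pregnancy", so many of these women will be using contraception already, and it notes that "the systemic absorption from a topical eye drop is low". All of this stands, and it sets the weight of the point. It does not remove the gap, because the protocol itself provides for women of childbearing age and admits anyone above 18.

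Three stronger readings are tempting, and the documents do not support them.

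- **That a woman known to be pregnant could be started on ripasudil.** The contraindication in section 5.2.1 carries no time limit and already bars this. Section 7.1 gives the investigator the decision on significant findings after enrolment, and sections 6.1.2 and 6.5 let the treating physician change therapy. Only the unrecognised pregnancy remains.
- **That the wider diagnoses in DETECT I bring in younger women.** Section 5.1 admits iridocorneal endothelial syndrome, posterior polymorphous dystrophy and failed grafts, but nothing in the protocol says these patients are younger. DETECT II takes only Fuchs dystrophy.
- **That no test is done before surgery.** Pre-operative steps may sit in the Manual of Operations and Procedures, which is not available here. The point is that the protocol does not specify one.

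**Conclusion.** The point holds as a minor one. Following the protocol's stated rules, a woman with an unrecognised pregnancy conceived during the wait for surgery could start a drug that the protocol calls contraindicated in pregnancy. The interval is up to 20 days from enrolment to first dose under the Schedule of Activities, and weeks to months under section 5.4.

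Very few participants are likely to be affected. The risk of 0.003 to 0.037 per woman rests entirely on the assumed wait and conception rate, and section 8.3.9's definition points to the lower end. The number of women concerned cannot be taken from the protocol; the expected age range suggests a handful at most. That there is a single test is inferred from the wording of 5.2.1 and 8.3.9 and from the absence of any test in the schedule. Endpoints, power and inference are unaffected.

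**What to change.** 1. In sections 5.2.1 and 8.3.9, require contraception from the enrolment test to the end of the three-month ripasudil or placebo course, for all women of childbearing age whatever their arm, because assignment is masked.
2. In the same sections, repeat the urine test shortly before randomisation, or at the latest at Visit 2, and require a negative result before the first dose.
3. List both tests in the Schedule of Activities.

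Testing before randomisation is preferable. A positive result is then a screen failure under section 5.4, before tissue has been prepared or drops shipped. If randomisation is done well ahead of surgery, Visit 2 is closer to the first dose, but a positive result there comes after the tissue is ready and could waste a graft if surgery is deferred.

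The cost is a few sentences, two schedule entries and one extra dipstick for a handful of women. No visit is added if the test is done at Visit 2 or at an existing pre-operative contact. No separate rule for a known pregnancy is needed, since the contraindication and section 7.1 largely cover it.

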5.3 LIFESTYLE CONSIDERATIONS

None.

5.4 SCREEN FAILURES

Screen failures are defined as participants who consent to participate in the clinical trial but are not subsequently randomly assigned to the study intervention or entered in the study. A minimal set of screen failure information is required to ensure transparent reporting of screen failure participants, to meet the Consolidated Standards of Reporting Trials (CONSORT) publishing requirements and to respond to queries from regulatory authorities. Minimal information includes demography, screen failure details, eligibility criteria, and any serious adverse event (SAE).

In this study, all patients who are randomized will be included in the primary analysis, regardless of whether or not they actually receive the assigned intervention. Randomization will occur just days before the participant's surgery to ensure that all randomized patients receive their assigned surgical intervention. Due to the nature of the intervention, patients may have weeks to months between enrollment in the study and randomization/surgery, leaving time for patients to drop out of the study before randomization. All required information will be collected from screen failures.

DETECT

Version 5.0
21 March 2023

5.5 STRATEGIES FOR RECRUITMENT AND RETENTION

Patients with diseased or damaged endothelium from Fuchs Endothelial Dystrophy or Pseudophakic Bullous Keratopathy will be recruited from the cornea subspecialty clinics of participating institutions for inclusion in the study. For eligible patients the study will be explained in English or the patient's native language using a translator for non-English speakers, in addition to the risks and benefits of participating in the study. The patients will be assured that they can receive all appropriate treatment whether or not they participate in the study. The side effects and drug interaction of all study drugs as well as endothelial keratoplasty are also explained in the consent forms. The study personnel (the study ophthalmologist with the help of the study coordinator) will make sure the patient understands risks, benefits and responsibilities of participating in this trial. Then the study personnel will obtain the patient signature on the consent form.

After the initial screening visit, this trial includes 6 study visits over 24 months. These study visits are:

1. Baseline (pre-operative)
2. Surgery
3. 3 Month Follow-Up (visit window: 2-4 months post-surgery)
4. 6 Month Follow-Up (visit window: 5-7 months post-surgery)
5. 12 Month Follow-Up (visit window: 10-14 months post-surgery)
6. 24 Month Follow-Up (visit window: 20-28 months post-surgery)

For both trials, patients will be randomized by the eye bank one week prior to surgery. At each visit, the study coordinator will work with the patient to schedule their next study visit. The study coordinator will give the patient written documentation of their upcoming visits, and will follow-up with a phone call as their appointments approach. Using this retention strategy, the DETECT-TES had 100% follow-up at 12 months. We are confident that these studies will have high retention as well.

6 STUDY INTERVENTION

6.1 STUDY INTERVENTION(S) ADMINISTRATION

6.1.1 STUDY INTERVENTION DESCRIPTION

Ultrathin Descemet stripping automated endothelial keratoplasty (UT-DSAEK)

Tissue grafts will be cut to the right thickness using a microkeratome prepared at the eye bank per standard eye bank protocol (about 60-90 microns). The grafts will be punched in the operating room to 7.0- 7.5 mm. A 4 mm corneal incision will be used, with Endoserter as the means of inserting the graft, an FDA approved device for this purpose. Donor tissue or media will be sent for fungal culture by the enrollment site.

Descemet membrane endothelial keratoplasty (DMEK)

Endothelial grafts will be pre-peeled at the eye bank, pre-punched to 7.0 - 7.5 mm and pre-loaded at the eye bank. The endothelium will be stained with trypan blue. The recipient descemets membrane will be stripped to 7.0 - 7.5 mm. A 2.4 mm corneal incision will be used and the graft will be inserted with a modified Jones tube injector, micro Jones tube injector, LEITR glass cannula, micro Stephens glass cannula, or Geuder cannula. The tap technique will be used to position the graft. Donor tissue or media will be sent for fungal culture by the enrollment site.

Descemet Stripping Only (DSO)

The pupil center will be marked in mesopic conditions to guide centration. A 4mm diameter imprint centered on the central mark will be used to guide the descemetorhexis. A reverse sinskey hook will be used to gently initiate a tear in Descemet's membrane and Gorovoy DSO forceps (or similar instrument) will be used to complete the descemetorrhexis

DETECT

Version 5.0
21 March 2023

without disturbing the underlying stroma. The central endothelium will then be gently peeled and removed with forceps.

Ripasudil 0.4%

Ripasudil 0.4% is a selective rho-kinase (ROCK) inhibitor that has been shown to promote endothelial cell proliferation. Patients randomized to receive topical ripasudil will begin medication on post-op day 1. They will take this medication 4 times per day for 3 months.

Placebo

For participants randomized to placebo, they will receive topical placebo in place of topical ripasudil. The placebo will be sodium chloride 0.9%. Those randomized to placebo will receive the topical placebo on the same medication schedule described above for ripasudil.

6.1.2 DOSING AND ADMINISTRATION

The schedule of medications for the studies are below:

DETECT I Dosing schedule for medications

Medication	Day 1-8	Day 9 – 30	Month 2-3	Month 4	Month 5	Month 6- 12
Ripasudil 0.4% or placebo	4x/day	4x/day	4x/day			
Prednisolone	4x/day	4x/day	4x/day	3x/day	2x/day	1x/day
Ofloxacin	4x/day					

DETECT II Dosing schedule for medications

Medication	Day 1 – 8	Day 9-30	Month 2	Month 3	Month 4	Month 5	Month 6-24
DSO-R Ripasudil 0.4%	4x/day	4x/day	4x/day	4x/day			
Dexamethasone 0.1%	4x/day	4x/day					
(Dexamethasone) placebo			4x/day	4x/day	3x/day	2x/day	1x/day
Ofloxacin	4x/day						
DMEK (Ripasudil) placebo	4x/day	4x/day	4x/day	4x/day			
Dexamethasone 0.1%	4x/day	4x/day	4x/day	4x/day	3x/day	2x/day	1x/day
Ofloxacin	4x/day						

DETECT

Version 5.0
21 March 2023

Participants randomized to receive topical placebo instead of topical ROCK-inhibitors will receive the placebo on the same medication schedule as ripasudil outlined above. If at any time the masked treating physician deems it appropriate to change the patient's treatment, he/she may do so.

